### 1.3. Schedule of Activities (SoA)

The SoA table provides an overview of the protocol visits and procedures. Refer to the [STUDY ASSESSMENTS AND PROCEDURES](#) section of the protocol for detailed information on each procedure and assessment required for compliance with the protocol.

The investigator may schedule visits (unplanned visits) in addition to those listed in the SoA table, in order to conduct evaluations or assessments required to protect the well-being of the participant.

Study related visits and procedures may be disrupted during the Coronavirus Disease 2019 (COVID-19) pandemic, please see [Appendix 11](#) for alternative solutions, if applicable.

Study Period	Screen	Treatment Period 1 (Lead In)			Treatment Period 2	Treatment Period 3	Treatment Period 4						Safety Follow up
		1	2 (BL)	3			4	5	6	7	8	9	
Visit Identifier	1	2 (BL)	3	4	5	6	7	8	9	10	PK Profile Phlebotomy 	11 (EOT/ET) 	12 
Study Week 	-6 to -1	0	4	10	16	22	24	26	28	30	30, 31	32	36
Study Day	-42 to -1	1	29	71	113	155	169	183	197	211	211 - 224	225	253
Visit Window in Days			±7	±7	±7	±7	±7	±7	±7	±7	[±1]	±1	+14
Informed Consent	X												
Inclusion/Exclusion Criteria	X	X											
Contraception check	X												
Medical History	X												
Demography	X												
Prior Treatments for RA	X												
HIV, Hepatitis B & C 	X												
FSH 	X												
Tuberculosis Test 	X												
Chest Radiography 	X												
Single ECG (12-Lead)	X												
Participant ID number (IWRS) 	X												
Randomization (IWRS) 				X									
Complete Physical Examination 	X											X 	
Vital Signs 	X	X		X								X	
Body Weight 	X	X		X 								X	

Study Period	Screen	Treatment Period 1 (Lead In)			Treatment Period 2	Treatment Period 3	Treatment Period 4						Safety Follow up
		1	2 (BL)	3			4	5	6	7	8	9	
Visit Identifier	1	2 (BL)	3	4	5	6	7	8	9	10	PK Profile Phlebotomy 	11 (EOT/ET) 	12 
Study Week 	-6 to -1	0	4	10	16	22	24	26	28	30	30, 31	32	36
Study Day	-42 to -1	1	29	71	113	155	169	183	197	211	211 - 224	225	253
Visit Window in Days			±7	±7	±7	±7	±7	±7	±7	±7	[±1]	±1	+14
Pregnancy Test 	X	X										X	
Contraception Verification		X											
Safety Laboratory	Hematology	X	X	X								X	
	Chemistry	X	X	X								X	

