## 4. STUDY DESIGN

### 4.1. Overall Design

This is an open-label, multi-national, 2-arm, randomized, parallel-group study designed to evaluate the interchangeability of the switching arm (PF-06410293 and Humira), compared to non-switching arm (Humira), in participants with moderately to severely active RA on background methotrexate (MTX). For purposes of this protocol, the treatment arm that includes switches between PF-06410293 and Humira will be referred to as the “switching” arm, while the treatment arm that comprises continuous Humira treatment will be referred to as the “non-switching” arm.

This study will enroll a maximum of approximately 420 participants such that approximately 314 evaluable participants complete the study.

Study treatment will be provided through 4 treatment periods. For the first 10 weeks, all participants will receive Humira [Treatment Period (TP) 1]. Upon completion of TP1, participants will be randomized (1:1 ratio) into either the switching or the non-switching arm prior to dosing on Week 10. Randomization will be stratified by 3 body weight groups (Week 10 weight) ( $\geq 40$  kg to  $< 70$  kg;  $\geq 70$  kg to  $< 100$  kg;  $\geq 100$  kg to  $\leq 130$  kg). Participants randomized to the non-switching arm will continue on Humira for the remainder of the study, and participants randomized to the switching arm will continue switching in each TP (TP2: PF-06410293; TP3: Humira; TP4: PF-06410293).

- TP1 (Lead In Period) will begin with the first dose of investigational product on Week 0 (Day 1) and conclude with the completion of Week 10 pre-dose assessments.
- TP2 will begin with the 1:1 randomization of the participants to either the switching arm or the non-switching arm at Week 10. Investigational product dosing for Week 10 will begin after the randomization process in the respective treatment arms and will conclude with the completion of Week 16 pre-dose assessments.

- TP3 will begin with investigational product dosing on Week 16, and conclude with the completion of Week 22 pre-dose assessments.
- TP4 will begin with investigational product dosing on Week 22 and continue through Week 30, where onsite investigational product dosing is scheduled at Weeks 22, 24, 26, 28, and 30, followed by a 2-week PK sampling period from Week 30 to Week 32. TP4 will conclude with end of treatment (EoT) assessments and final dose administration at Week 32.

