### **Other Exclusions:**

23. Investigator site staff members directly involved in the conduct of the study and their family members, site staff members otherwise supervised by the investigator, or Pfizer employees, including their family members, directly involved in the conduct of the study.
24. Pregnant females and breastfeeding females, male participants with partners currently pregnant who are unwilling to use a condom, or male and female participants of childbearing potential who are unwilling or unable to use an effective method of contraception as outlined in this protocol for the duration of the study and for at least 5 months after the last dose of investigational product.

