#### **5.3.1. Contraception**

The investigator or his or her designee, in consultation with the participant, will confirm that the participant has selected an appropriate method of contraception for the individual participant and his or her partner(s) from the permitted list of contraception methods (see [Appendix 4](#) and [Section 10.4.4](#)) and will confirm that the participant has been instructed in its consistent and correct use. At time points indicated in the [SoA](#), the investigator or designee will inform the participant of the need to use effective contraception consistently and correctly and document the conversation and the participant's affirmation in the participant's chart (participants need to affirm their consistent and correct use of at least 1 of the selected methods of contraception). In addition, the investigator or designee will instruct the participant to call immediately if the selected contraception method is discontinued or if pregnancy is known or suspected in the participant or partner.

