Participants previously treated for active TB infection, must have completed and documented a successful course of treatment in accordance with local guidelines. Participants detected with latent TB at Screening are eligible providing they have received at least 4 weeks of chemoprophylaxis and commit to completion of the full course of treatment, in accordance with local standard of care, before starting the study treatment. Participants whose chest radiography (or alternative chest imaging) and QuantiFERON®-TB Gold In-Tube Test results indicate no evidence of TB infection, but who are considered by the investigator to be at high risk to develop tuberculosis (eg, residing in high-risk areas or travel to high-risk areas), may be started on a course of TB prophylaxis or treatment in accordance with local guidelines at the discretion of the investigator. If TB prophylaxis treatment is started after the Screening visit, aminotransferases (ALT/AST) levels should be checked within at least 4 weeks prior to first investigational product in TP1 to confirm results fulfill entry criteria.

It is recommended that participants avoid changing prescription or non-prescription drugs, vitamins, and dietary supplements within 7 days or 5 half-lives (whichever is longer) prior to the first dose of investigational product and prior to study visits unless otherwise noted below, throughout the study.

Concomitant medications will be collected at each visit/contact from the time the consent form is signed to the final study visit/contact. All concomitant medication taken during the study (prescription, non-prescription drugs, and non-drug therapy as appropriate) must be recorded on the eCRF with daily dose, and start and stop dates of administration. If a participant discontinues early, concomitant medications must be followed at the EoT visit, the safety follow-up visit at least 28 calendar days after the last dose of investigational product, and any additional post-treatment phone contact and/or extended safety follow-up.

Concomitant medications prohibited in the study are summarized in [Appendix 10](#).

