## **6.5.1. Stable Background Therapies**

### **6.5.1.1. Methotrexate**

Adalimumab must be administered concomitantly with a stable dose of MTX throughout the course of study treatment.

The administration of MTX, including dosage, laboratory testing, follow-up care (including contraception requirements), and contraindications should be performed according to local standards of care throughout the study.

At study entry, participants must have received oral or IM MTX for at least 12 weeks and have been on a stable dose of 10 to 25 mg per week for at least 4 weeks prior to first dose of investigational product. In geographic regions where 6 mg per week is a recommended initial dose by local guidance or standard of care, a stable dose of as low as 6 mg per week for at least 4 weeks prior to first dose of investigational product will be permitted.

Participants are required to continue their stable dose of MTX background therapy throughout the study. Dose reduction of MTX therapy during the study treatment is not recommended, with the exception of significant intolerance, and the dose reduction must be documented with the investigator's medical justification. Participants will not be discontinued from study treatment following a justified dose reduction of MTX, unless the MTX is adjusted below the minimal required dosage level of 7.5 mg/week (or a dose as low as 6 mg/week in geographic regions where permitted by local guidance or standard of care).

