- AEs, contraception use and concomitant medications will be collected by study site investigator(s)/staff remotely, eg by phone for each remote visit and entered timely in the eCRF.
- For participant discontinuation reporting in the CRF: select the most appropriate status for discontinuation; if the discontinuation is associated with the current COVID-19 pandemic, enter "COVID-19" in the "Specify Status" field.

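### The Schedule of Activities has no on-site contraception check after Day 1, although remote visits include one and contraception is required for at least five months after the Week 32 dose

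*Protocol*

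**What the plan says.** The SoA (Protocol Section 1.3) has two contraception rows. "Contraception check" carries one mark, at Screening. "Contraception Verification" carries one mark, at Visit 2 (Day 1). Neither row is marked from Week 4 to Week 36.

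Section 5.3.1 relies on those rows. At the SoA time points the investigator or designee "will inform the participant of the need to use effective contraception consistently and correctly", records the conversation, and obtains the participant's affirmation of use.

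Appendix 11 applies only during the COVID-19 pandemic. It states: "AEs, contraception use and concomitant medications will be collected by study site investigator(s)/staff remotely, eg by phone for each remote visit", with entry in the eCRF.

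Exclusion criterion 24 requires an effective method "for the duration of the study and for at least 5 months after the last dose of investigational product". Section 10.4.2 repeats the five months for women of childbearing potential. The last dose is given at Week 32 (Section 4.1: "TP4 will conclude with end of treatment (EoT) assessments and final dose administration at Week 32"), and the last scheduled contact is Week 36.

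**The concern.** The same visit includes a contraception question if held by telephone and has none scheduled if held on site. Appendix 11 names three items together: adverse events, contraception use and concomitant medications. The SoA schedules the first and third at every on-site visit but not the second, and the protocol gives no reason.

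Participants receive adalimumab on top of methotrexate. SoA footnote 1 places assessments before dosing unless otherwise stated, so the Day 1 verification normally precedes the first injection. On a literal reading, no scheduled on-site question about contraception is asked once exposure has begun. A lapse in abstinence or in a barrier method could go unnoticed until the Week 32 pregnancy test. The longest part of the obligation, after the last dose, begins with no scheduled reminder.

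**Working it through.** No power, alpha or sample-size figure bears on this point. The check compares the SoA with the related sections and counts days.

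**Are the SoA rows readable?** The neighbouring Pregnancy Test row shows Screening, Day 1 and Week 32, as expected. The adverse-event and concomitant-medication rows are marked throughout. Nothing suggests that marks were lost from the two contraception rows.

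**Contacts after Day 1 without a contraception entry.** Leaving out the column for PK phlebotomy only, these are Weeks 4, 10, 16, 22, 24, 26, 28, 30, 32 and 36, which is 10. Week 32 has a pregnancy test and Week 36 follows the last dose, so 10 − 2 = 8 contacts during dosing have neither a contraception check nor a scheduled pregnancy test.

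**Interval between scheduled pregnancy tests.** Day 225 − Day 1 = 224 days, and 224 / 7 = 32 weeks.

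**Required contraception beyond the last contact.** Inputs are the last dose at Day 225, the Week 36 contact at Day 253 with a +14-day window (so up to Day 267), and five months taken as 150 to 153 days (an assumption).

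- End of requirement: 225 + 150 = Day 375, to 225 + 153 = Day 378.
- Shortest interval after the last contact: 375 − 267 = 108 days.
- Longest interval: 378 − 253 = 125 days.
- In weeks: 108 / 7 ≈ 15 and 125 / 7 ≈ 18.

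**Could concomitant-medication review stand in for a contraception question?** Section 10.4.4 lists 12 methods.

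| Type | Items in Section 10.4.4 | Count |
|---|---|---|
| Hormonal | 1, 3, 6, 7, 9 | 5 |
| Non-hormonal | 2, 4, 5, 8, 10, 11, 12 | 7 |
| Non-hormonal and dependent on continued use | 8, 10, 11, 12 | 4 |

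Medication dates may show that a hormonal method was stopped. They would not reliably show a lapse in abstinence, condom use, a cap, diaphragm or sponge, or double-barrier use.

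**The case against.** The strongest reply is that Appendix 11 creates nothing new. It adapts existing procedures, and its sentence may only move to the telephone a question that sites already ask at each visit. The case report form would settle this, but it is not among the documents. The consent document is also unavailable and may state the five-month rule. Both points limit what can be said about practice. They do not change the fact that the protocol's own schedule has no on-site check after Day 1.

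The protocol also has other controls:

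- Section 6.5.1.1 says that methotrexate "follow-up care (including contraception requirements), and contraindications should be performed according to local standards of care throughout the study".
- Section 6.5 states: "Concomitant medications will be collected at each visit/contact from the time the consent form is signed to the final study visit/contact".
- Section 5.3.1 tells participants to call at once if a method stops or pregnancy is suspected.
- Section 8.2.7 requires a pregnancy test after a missed cycle.
- Section 8.3.5.1 collects pregnancies until 50 to 100 days after the last dose, which is 22 to 72 days past nominal Week 36 (50 − 28 and 100 − 28).

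These reduce the risk. However, none schedules a study question about contraception, and the last two concern pregnancy that is suspected or has occurred.

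Two smaller objections stand. Counting methods is not counting users: three of the seven non-hormonal methods (IUD, tubal occlusion, vasectomized partner) do not depend on daily behaviour, and item 12 combines a condom with an item 11 method. In addition, Section 10.4.1 mandates no specific male measures, so the point mainly concerns women of childbearing potential.

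**Conclusion.** The concern holds as a minor safety-monitoring gap and an inconsistency between on-site and remote visits. Ten contacts after Day 1 have no contraception entry; eight of these fall during dosing and have no scheduled pregnancy test. Required contraception extends about 108 to 125 days past the last contact, taking five months as 150 to 153 days. The documents give neither the number of participants of childbearing potential nor a lapse rate, so no number of exposed pregnancies can be estimated. The primary PK analysis and the sample size are unaffected. Correcting this is a cheap improvement; the trial's conclusions do not depend on it.

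**What to change.** In the SoA, mark the existing contraception-check row at Weeks 4, 10, 16, 22, 24, 26, 28, 30, 32 and 36 for participants of childbearing potential. The question is then asked and recorded at the same contacts whether on site or remote, alongside the adverse-event and concomitant-medication questions already scheduled there. Section 5.3.1 needs no rewording, because it already defers to the SoA. At Weeks 32 and 36, add a reminder that contraception must continue for at least five months after the last dose.

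The cost is an SoA row change and one short eCRF question per existing contact; Appendix 11 already sends this item to the eCRF for remote visits. No visit, test or staff is added. The change needs a protocol amendment with the ethics approval described in Section 10.1.1, so it is best included in the next amendment.

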## 10.12. Appendix 12: Abbreviations

The following is a list of abbreviations that may be used in the protocol.

Abbreviation	Term
6-MP	6 mercaptopurine
ACR	American College of Rheumatology
Abd	Abdominal
Abs	Absolute
ACR	American College of Rheumatology
ADA	antidrug antibodies
AE	adverse event
ALT	alanine aminotransferase
ANC	Absolute neutrophil count
AS	ankylosing spondylitis
AST	aspartate aminotransferase
AUC	area under the concentration - time curve
AUC τ	area under the concentration - time curve over the dosing interval
AV	Atrioventricular
BA	Bioavailability
BBS	Biospecimen Banking System
BE	Bioequivalence
β-hCG	beta-human chorionic gonadotropin
BMI	Body mass index
BP	blood pressure
Bpm	beats per minute
BUN	blood urea nitrogen
C av	average concentration
CD	Crohn's disease
CFR	Code of Federal Regulations
CHF	congestive heart failure
COVID-19	Coronavirus Disease 2019
CIOMS	Council for International Organizations of Medical Sciences
CK	creatine kinase
CL/F	apparent clearance
C max	maximum observed concentration
CMC	Chemistry, Manufacturing, and Controls
CO 2	carbon dioxide (bicarbonate)
CONSORT	Consolidated Standards of Reporting Trials
COX-2	Cyclooxygenase-2
CRF	case report form
CRO	contract research organization
CRU	clinical research unit
CSF	cerebrospinal fluid
CSR	clinical study report

Abbreviation	Term
CT	clinical trial
CT	computed tomography
CTMS	clinical trial management system
C trough	predose concentration during multiple dosing
CV	Cardiovascular
CV	Coefficient of variation
DCT	data collection tool
DILI	drug-induced liver injury
DMARD	Disease modifying anti-rheumatic drug
DMC	data monitoring committee
DNA	deoxyribonucleic acid
DRE	disease-related event
DU	dispensable unit
EBV	Epstein Barr virus
EC	ethics committee
ECL	Electrochemoluminescent
ECG	Electrocardiogram
eCRF	electronic case report form
E-DMC	external data monitoring committee
EDP	exposure during pregnancy
EDR	extemporaneous dispensing record
ELISA	enzyme linked immunosorbent assay
EMA	European Medicines Agency
EoT	End of Treatment
ET	Early Termination
EU	European Union
EudraCT	European Clinical Trials Database
EULAR	European League Against Rheumatism
FAP	Final Approved Protocol
FDA	United States (US) Food and Drug Administration
FK506	Tacrolimus
FSH	follicle-stimulating hormone
GCP	Good Clinical Practice
GGT	gamma-glutamyl transferase
H	Hour
HbA 1c	hemoglobin A 1c
HBcAb	hepatitis B core antibody
HBsAb	hepatitis B surface antibody
HBsAg	hepatitis B surface antigen
HCG	human chorionic gonadotropin
HCL	Hydrogen chloride
HCV	hepatitis C
HCVAb	hepatitis C antibody

Abbreviation	Term
HCV RNA	HCV riboneucleic acid
HEENT	head, eyes, ears, nose and throat
Hgb	Hemoglobin
HIPAA	Health Insurance Portability and Accountability Act
HIV	human immunodeficiency virus
HPV	human papilloma virus
HRT	hormone replacement therapy
HS	hidradenitis suppurativa
IA	intra articular
IB	investigator's brochure
IC	Interchangeability
ICD	informed consent document
ICH	International Council for Harmonisation
ID	Identification
IFU	Instruction for Use
IgG1	Immunoglobulin G1
IM	Intramuscular
IMP	investigational medicinal product
IND	investigational new drug application
Inj	injection
INR	international normalized ratio
IP	investigational product
IP manual	investigational product manual
IRB	institutional review board
IRC	internal review committee
IRT	interactive response technology
ISR	injection-site reactions
ITT	intent-to-treat
IUD	intrauterine device
IUS	intrauterine hormone-releasing system
IVIG	IV immunoglobulin
IWRS	interactive Web-based response system
JAK	janus kinase inhibitor
LBBB	left bundle branch block
LDAS	low disease activity state
LFT	liver function test
mAb	monoclonal antibody
MCH	mean corpuscular hemoglobin
MCHC	mean corpuscular hemoglobin concentration
MCV	mean corpuscular volume
MedDRA	Medical dictionary for regulatory activities
MnB	Neisseria meningitidis serogroup B
Msec	Millisecond

Abbreviation	Term
MTX	Methotrexate
N/A	not applicable
Nab	neutralizing antibodies
NIMP	noninvestigational medicinal product
NMSC	Non-Melanoma Skin Cancer
NOAEL	no-observed-adverse-effect level
NYHA	New York Heart Association
PACLS	Protocol Administrative Clarification Letters
CCI	
PCD	primary completion date
PD	pharmacodynamic(s)
PFS	prefilled syringe
PFP	pre-filled pen
PI	principal investigator
PK	pharmacokinetic(s)
PS	plaque psoriasis
PSA	psoriatic arthritis
PT	prothrombin time
PVC	premature ventricular contraction/complex
QTc	corrected QT
QTcF	corrected QT (Fridericia method)
QFT	QuantiFERON® - TB Gold In-Tube test
Qual	qualitative
RA	rheumatoid arthritis
RBC	red blood cell
RNA	ribonucleic acid
SAE	serious adverse event
SAP	statistical analysis plan
SC	subcutaneous
SEER	Surveillance, Epidemiology, and End Results
SmPC	Summary of Product characteristics
SMQ	standardized MedDRA query
SoA	schedule of activities
SOP	standard operating procedure
SRSD	single reference safety document
SToD	study team on demand
SUSAR	suspected unexpected serious adverse reaction
TB	tuberculosis
TBili	total bilirubin
TEAE	treatment-emergent adverse event
T max	time at which C max occurs
TNF	Tumor necrosis factor
TP	treatment periods

Abbreviation	Term
TP1	treatment period 1
TP2	treatment period 2
TP3	treatment period 3
TP4	treatment period 4
UC	ulcerative colitis
ULN	upper limit of normal
US	United States
USPI	US Prescribing Information
UV	uveitis
WBC	white blood cell
WHO	World Health Organization
Wk	week
WOCBP	woman of childbearing potential

**1. VERSION HISTORY**

Table 1. Summary of Changes			
Version/ Date	Associated Protocol Amendment	Rationale	Specific Changes
1 29 Aug 2019	Original 28 Jun 2019	N/A	N/A
2. draft	Amendment 1 19 May 2020	Update to align with protocol amendment 1 and clarification/simplification/completion of prior version	
 
• Update the following sections to align with protocol amendment 1:                             
 
▪ Text update in the protocol title.
 
▪ Study design for TP4 and follow-up period (Section 2.2)
 
▪ The definitions of PK population (Section 4)
 
▪ The definition of treatment-emergent AEs (Section 3.5.1 and Section 6.1.3)
 
▪ The removal of TP2 to TP3 cumulative AE summary
 
 
 
• Update/provide more details on AESI definition and immunogenic AE definition and medical evaluation (Section 3.5.1).
 
• Exclude all subjects at site CCI from all the analysis populations due to violation of GCP principles (Section 4)
 
• More details on Hypothesis and Decision rule (Section 5.1)
 
• The analyses for Ctrough in TP1 and TP2-TP4 are combined as TP1-TP4 analysis using safety-randomized population (Section 6.2.1).
 
• Update/provide more detailed on ADA and NAb analysis (Section 6.2.2)
 
• Clarification/simplification of TP1 AE summary and provide more details on TP2 to TP4 AE summary including AESI and immunogenic AE (Section 6.6.1.1 and Section 6.6.1.2).
 

			
 
• Clarification/simplification of Lab data analysis for TP1 and TP2-TP4.
 
• Add COVID-19 related summary and analysis for protocol deviation, subject discontinuation, AE (Section 6.6.4)
 
• Removal of the following analyses which won't impact the study conclusion: demographic summary for Safety-TP1 population and Safety-randomized population; concomitant medication and non-drug treatment summary for TP1 data; vital sign analysis for TP1 data; physical examination, MTX dose and medical history.
 
• Additional typographic errors correction and editorial changes as necessary throughout the SAP.
 

--	--	--	--

